## **8.3 Primary Efficacy Endpoint(s) and Analyses**

### **8.3.1 Primary Efficacy Endpoint(s)**

The primary endpoint is the absolute change from Baseline through Day 29 in ppFEV1. The predicted values of FEV1 (L) at all study visits will be estimated for age, gender, and height using the 2012 Global Lungs Initiative equation. Percent predicted FEV1 is the ratio of FEV1 (L) to the predicted FEV1 (L), expressed as a percentage. For the primary efficacy endpoint in both Part 1 and Part 2, the corresponding statistical null hypotheses are that there is no difference in the mean value of ppFEV1 from baseline through Day 29 within each treatment group.

### **8.3.2 Handling of Missing Data for the Primary Efficacy Endpoint(s)**

Missing data will be handled using MMRM method as described in Section 8.2.

### **8.3.3 Primary Efficacy Analysis**

The primary analysis will be performed using MMRM with change from Baseline in ppFEV1 as the dependent variable. The mixed model includes the categorical fixed effects of treatment, visit and treatment-by-visit interaction, as well as the continuous fixed effect of baseline ppFEV1. The random effects of the model will be subject ID. Parameter estimation will use the method of restrictive maximum likelihood (REML).

The point estimate for the primary endpoint from the MMRM model along with the 95% confidence interval and the corresponding p-value will be presented for the primary efficacy analysis. The pairwise comparison of the primary endpoint of ppFEV1 between each active treatment group versus the placebo group will also be estimated using the same model. The Least Squares Mean of the treatment difference between each active treatment group versus the placebo group will be presented along with the 95% confidence interval and a 2-sided p-value.

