APPENDIX D. ACTIVITY SCHEDULE

The following table shows the required activities across the study visits. The individual activities are described in further detail in the Operations Manual.

Study Activities Table

Activity	Screening Period	Treatment Period				Follow-Up Period
	UP to Day -30	Day 1	Day 7 (phone call) (± 2 days)	Day 15 (± 2 days)	Day 29 (± 2 days) or Premature Discontinuation	30-Day Follow-Up (± 7 days)
INTERVIEWS & QUESTIONNAIRES						
Informed consent	✓					
Eligibility criteria	✓	✓				
Medical/surgical history	✓					
Adverse event assessment	✓	✓	✓	✓	✓	✓
Prior/concomitant therapy	✓	✓	✓	✓	✓	✓
Time of last dose of bronchodilator (if applicable)	✓	✓		✓	✓	✓
Date and time of previous 3 doses of study drug				✓	✓	
LOCAL LABS & EXAMS						
Height	✓					
Weight	✓	✓			✓	✓
Vital signs (include oral temperature, respiratory rate, heart rate, and blood pressure)	✓	✓		✓	✓	✓
Pulse oximetry	✓	✓		✓	✓	✓
Physical examination (full)	✓					
Physical examination (limited to throat, chest, heart)		✓		✓	✓	✓
Urine pregnancy test (females of childbearing potential only; to be followed by serum pregnancy test only if urine test is positive)		✓			✓	✓
12-lead ECG (after at least 5 minutes of rest while supine)	✓			✓	✓	
Sweat collection (send sample to central laboratory)	✓	✓		✓	✓	✓
Spirometry (on Days 1 and 15, pre-dose [0 hr] and 3 - 5 hr following dose). Numbers in parentheses indicate the number of tests.	✓	✓ (2)		✓ (2)	✓	✓
CENTRAL LABS						
CFTR Genotyping	✓					

Activity	Screening Period	Treatment Period				Follow-Up Period
	UP to Day -30	Day 1	Day 7 (phone call) (± 2 days)	Day 15 (± 2 days)	Day 29 (± 2 days) or Premature Discontinuation	30-Day Follow-Up (± 7 days)
Urine test for drugs of abuse	✓					
Serology for HBsAg, HCV, HIV-1 and HIV-2 antibodies	✓					
Serum pregnancy test (females of childbearing potential only)	✓					
High-sensitivity C-reactive protein (hsCRP), clinical chemistry, hematology (complete blood count), urinalysis	✓	✓		✓	✓	✓
Follicle-stimulating hormone (FSH) (postmenopausal females ≤ age 55 years only)	✓					
Blood samples for ABBV-3067 and ABBV-2222 pharmacokinetic assay (Day 15 samples pre-dose [0 hour], 2, 4, and 6 hours following dose; Day 29 approx. 24 hours following last dose). Numbers in parentheses indicate the number of samples to be drawn.				✓ (4)	✓ (1)	✓ (1)
Optional biomarker sample: Whole blood		✓			✓	
Rx TREATMENT						
Randomization/drug assignment		✓				
Dispense study drugs		✓		✓		
Perform drug reconciliation				✓	✓	

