## **2.4 Sample Size Determination**

The power calculations are provided for the most potentially efficacious groups with the combination treatment for both Part 1 and Part 2 for the primary efficacy endpoint. Placebo groups from both Part 1 and Part 2 will be combined in the Part 2 efficacy analysis. A sample size of 18 subjects in a group will provide 80% power to detect a 5.3% absolute increase from Baseline in ppFEV1 for that group assuming a standard deviation of 7.5%. When comparing to the placebo group, a sample size of 18 subjects in both treated group and placebo group will provide 80% power (Part 1), or a sample size of 18 subjects in treated group and 27 subjects in placebo group will provide approximately 87% power (Part 2), to detect a 7.3% difference in ppFEV1 change from Baseline between a treated group and the placebo group assuming the standard deviation of 7.5% for change in ppFEV1 for both groups.

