## **8.0 Efficacy Analyses**

### **8.1 General Considerations**

All efficacy analyses will be conducted for the FAS. All tests will be 2-sided at an alpha level of 0.05. For each part of the study, the efficacy analysis will be performed after all ongoing subjects have completed the study part and the database has been locked.

For the primary efficacy endpoint, the null hypothesis that the within-group absolute change from baseline in ppFEV1 through Day 29 is zero will be tested for each treated group at 2-sided alpha of 0.05.

Unless otherwise specified, any subject who is randomized based on a wrong stratum will be analyzed according to the actual stratum to which the subject belongs.

"Baseline" refers to the last non-missing observation before the first administration of study drug.

Unless otherwise specified, continuous variables will be analyzed using Mixed-Effect Model Repeat Measurement (MMRM) method with the model based mean and standard error being provided. The Baseline and visit means will also be presented for each treatment group among subjects who have both Baseline and at least one post Baseline visit values. Treatment groups will be compared using MMRM model as described in Section 8.2. Point estimates and 95% CIs of mean change from Baseline within each treatment group, the difference between each active treatment group and placebo, and the difference between each combination therapy arm and the ABBV-3067 150 mg monotherapy arm (Part 1 only) will be provided. Note that both placebo arms in Part 1 and Part 2 will be combined into one placebo group for the Part 2 model comparison.

Plots of the primary endpoint and certain secondary endpoints by treatment group will be used to visualize the change of endpoint values over time and the difference between treatment groups.

Use of bronchodilator medications and/or airway clearance techniques may affect lung function measurements in the short term. Therefore, post-baseline spirometric measurement that are collected inconsistently with the conditions for the baseline spirometric measurement will be excluded from the efficacy analysis. For example, if baseline spirometric measurement was collected prior to bronchodilator use, then any spirometric measurement collected post bronchodilator use at a subsequent visit will be excluded from analysis.

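### The primary model omits the continuous Screening ppFEV1 already collected; adding it costs about 1% of variance and could cut contrast variance by about 0% up to a ceiling near 30%

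*SAP*

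**What the plan says.** SAP 8.3.3 states: "The mixed model includes the categorical fixed effects of treatment, visit and treatment-by-visit interaction". It adds baseline ppFEV1 as a continuous covariate and subject as the random effect. Protocol 7.3 gives the same model. In SAP 8.1, Baseline "refers to the last non-missing observation before the first administration of study drug", which is normally the Day 1 pre-dose reading.

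The spirometry row of Protocol Appendix D reads "Spirometry (on Days 1 and 15, pre-dose [0 hr] and 3 - 5 hr following dose", and it also marks a test at Screening. Screening ppFEV1 decides eligibility (Protocol 5.1, criterion 9) and stratifies randomisation at 70% (Protocol 5.8, SAP 2.3). Spirometry is centrally read (Operations Manual 3.13). SAP 7.1 lists the continuous Screening value for descriptive summary. The 70% stratum appears again only as a subgroup in SAP 8.6. Neither form of the variable is a model term.

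**The concern.** The outcome subtracts a single Day 1 reading, so the measurement error in that reading enters every subject's change. Adjusting for the same reading removes part of that error. A second pre-treatment reading gives a better estimate of the subject's usual level and can remove more.

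The Screening value is taken before randomisation, so adjusting for it cannot bias a comparison between arms. Its correlation with the Day 1 value does no harm, because neither coefficient is interpreted.

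Precision matters here. Arms have 9 or 18 subjects, efficacy is one basis for choosing doses, and the planned power against placebo in Part 1 is about 80% for a 7.3-point difference.

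**Working it through.** **1. The plan's own figures.** SAP 8.1: "All tests will be 2-sided at an alpha level of 0.05". For the within-group test, SAP 2.4 says "A sample size of 18 subjects in a group will provide 80% power to detect a 5.3% absolute increase from Baseline in" the primary endpoint; its SD is taken as 7.5 points. Against placebo, the section says "a sample size of 18 subjects in both treated group and placebo group will provide 80% power (Part 1"); for Part 2 the figure is "18 subjects in treated group and 27 subjects in placebo group will provide approximately 87% power (Part 2"). Both are for a 7.3-point difference. With the noncentral t distribution:

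- one sample, n = 18, 5.3/7.5: 80.7%
- 18 v 18, 7.3/7.5: 81.0%
- 18 v 27, 7.3/7.5: 87.8%

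The stated power is reproduced.

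**2. Model for the gain.** The only variance figure in the documents is the SD of 7.5. The rest is assumed:

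- a stable level T with between-subject SD 14
- independent visit errors with SD s
- variation in response with variance r², which Screening does not predict
- the constraint 2s² + r² = 7.5² = 56.25

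With k = 1 (Day 29 only) or k = 2 (mean of Days 15 and 29):

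- residual variance given Baseline B: Var(T|B) + s²/k + r², where Var(T|B) = 1/(1/196 + 1/s²)
- residual variance given B and Screening S: Var(T|B,S) + s²/k + r², where Var(T|B,S) = 1/(1/196 + 2/s²)

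Upper end, s = 5.3: s² = 28.09, r² = 56.25 − 56.18 = 0.07, Var(T|B) = 24.57, Var(T|B,S) = 13.11.

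- k = 2: 24.57 + 14.05 + 0.07 = 38.69 falls to 13.11 + 14.05 + 0.07 = 27.23, a cut of 29.6%.
- k = 1: 52.73 falls to 41.27, a cut of 21.7%.

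Lower noise, s = 2.5: s² = 6.25, r² = 43.75, Var(T|B) = 6.06, Var(T|B,S) = 3.08.

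- k = 2: 6.06 + 3.13 + 43.75 = 52.94 falls to 49.96, a cut of 5.6%.

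Percentage cut in residual variance:

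| s | Day 29 only | Mean of Days 15 and 29 | Day 29 only, Screening noise 1.5 times larger |
|---|---|---|---|
| 1.5 | 2.0 | 2.0 | 1.2 |
| 2.5 | 5.3 | 5.6 | 3.3 |
| 3.5 | 10.1 | 11.3 | 6.1 |
| 4.5 | 16.1 | 19.7 | 9.7 |
| 5.3 | 21.7 | 29.6 | 13.0 |

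Changing the between-subject SD from 10 to 17 moves the top figure for the two-visit mean from 26.7% to 30.7%. If lung function drifts slowly (correlation time 90 to 365 days) and visit noise is small (s = 1.5 to 2.5), the cut is only 0.2% to 3.3%.

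**3. Cost.** One more covariate inflates variance by about 1/(N − arms − 1). In Part 1 this is 1/(117 − 8 − 1) = 0.9%. In Part 2, with pooled placebo, it is 1/(90 − 5 − 1) = 1.2%.

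**4. Contrasts and within-arm means.** An arm's LS mean is evaluated at the overall covariate mean, which itself varies from sample to sample. The absolute fall in its sampling variance is therefore scaled by 1 − n/N: 1 − 18/117 = 0.85 for an 18-subject arm in Part 1, and 1 − 27/90 = 0.70 for pooled placebo in Part 2. A 4,000-run ANCOVA simulation with Part 1 arm sizes and Screening restricted to 40–90% gave these empirical cuts, with the cost in item 3 included:

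| s | Contrast, two-visit mean | Within-arm, two-visit mean | Contrast, Day 29 | Within-arm, Day 29 |
|---|---|---|---|---|
| 1.5 | 1.4% | 1.8% | 0.6% | 0.0% |
| 3.5 | 11.0% | 9.7% | 9.6% | 7.5% |
| 5.3 | 25.2% | 23.9% | 19.7% | 16.4% |

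Differences of a few tenths of a point are simulation noise.

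**5. What a cut would mean.** Take 7.5 as the residual SD of the planned model.

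- A 5% cut acts like 18/0.95 = 18.9 subjects per arm. Power rises to 82.9% (18 v 18) and 89.4% (18 v 27).
- A 30% cut acts like 18/0.70 = 25.7 per arm. Power rises to 92.4% and 96.2%, and the detectable difference falls from 7.3 to 7.3 × √0.70 = 6.1.

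**The case against.** The plan contains no error on this point. Protocol and SAP agree, the model already adjusts for the baseline value of the outcome, and the stated power holds without a second covariate. This is a dose-ranging Phase 2 study with no multiplicity procedure (SAP 12.0). All of that stands, and it makes this an improvement rather than a correction.

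Screening is also not an equivalent second baseline:

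- Consistent timing of bronchodilators and airway clearance relative to spirometry is asked for only from Day 1 (Protocol 5.4), and SAP 8.1 has no consistency rule for Screening.
- The first dose is timed to the start of an inhaled-antibiotic cycle, so Screening may fall in another phase of the cycle.
- Screening may be up to 30 days earlier.
- Retests and rescreening (Protocol 4.1) can leave more than one Screening value.

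These points also stand. They lower the likely gain and call for a selection rule, but they do not remove the case for the covariate.

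A reader might infer a dependable gain of at least 5%, reaching 30%, for every arm estimate and at no cost. The documents do not support that. They give no visit-to-visit correlation, so 5% is not a floor. The 30% needs all of the SD of 7.5 to be visit noise and needs Days 15 and 29 to be averaged, whereas SAP 8.3.1 does not say whether the endpoint through Day 29 is an average or a single visit. The primary hypothesis is within-group, where the true gain is smaller than for contrasts. If the covariate turns out to explain nothing, there is a net loss of about 1%.

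**Conclusion.** The point holds as a near-free gain in precision of uncertain size. The model uses one of two scheduled pre-treatment ppFEV1 values and leaves out the one that stratified randomisation. Adding it would lower the variance of active-versus-placebo contrasts by about 0% to about 30%. The top of the range falls to about 22% for Day 29 alone, and lower still if Screening is noisier than Day 1. Within-arm means gain somewhat less.

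The range rests on an assumed between-subject SD of 14 and an assumed split of the SD of 7.5 into visit noise and response variation. The documents do not allow it to be narrowed. The possible loss is about 1%, so the change is worth making. The planned analysis remains valid without it.

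**What to change.** Before unblinding, add continuous Screening ppFEV1 to SAP 8.3.3 as a fixed covariate beside baseline ppFEV1, and align Protocol 7.3. Keep the endpoint as change from the Day 1 baseline. State which Screening value is used: the qualifying value from the final screening or retest.

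The same can be done for FVC and FEF25-75 with their Screening values, which come from the same test. The gain for those endpoints was not computed.

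The sponsor can first estimate the Screening-to-Day 1 pre-dose correlation. The access restriction in Protocol 5.8 and SAP 2.3 covers only results after the first dose, so this needs no unblinding.

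Cost: a short text change in each document, the selection rule, and one degree of freedom (about 1% of variance). No new data, visit or subject is needed.

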7.3 Statistical Analyses for Efficacy

All efficacy analyses will be conducted on the FAS based on treatment as randomized.

For the primary efficacy endpoint in both Part 1 and Part 2, the null hypothesis that the within-group absolute change from baseline in ppFEV₁ through Day 29 is zero will be tested for each treated group at 2-sided alpha of 0.05. The primary analysis will be performed using a mixed-effect model with repeated measures (MMRM) with change from Baseline in ppFEV₁ as the dependent variable; treatment group, visit, and treatment-by-visit interaction as fixed effects; subject as a random effect; and baseline ppFEV₁ as a covariate. The estimate for the within-group mean change along with the 95% confidence intervals and the corresponding *P* values will be calculated as the primary analysis. The treatment effect compared to placebo will be estimated using the same model.

The secondary endpoints of sweat chloride, ppFEV₁, FVC, and FEF₂₅₋₇₅ will be analyzed based on an MMRM model similarly as the primary endpoint.

Details on the efficacy analyses are provided in the SAP.

Sample Size Estimation

The power calculations are provided for the most potentially efficacious groups with the combination treatment for both Part 1 and Part 2 for the primary efficacy endpoint. Placebo groups from both Part 1 and Part 2 will be combined in the Part 2 efficacy analysis. A sample size of 18 subjects in a group will provide 80% power to detect a 5.3% absolute increase from baseline in ppFEV₁ for that group assuming a standard deviation of 7.5%. When comparing to the placebo group, a sample size of 18 subjects in both treated group and placebo group will provide 80% power (Part 1), or a sample size of 18 subjects in treated group and 27 subjects in placebo group will provide approximately 87% power (Part 2), to detect a 7.3% effect size in ppFEV₁ change from Baseline assuming the standard deviation of 7.5% for change in ppFEV₁ for both groups.

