### 2.3 Treatment Assignment and Blinding

All subjects will be assigned a unique identification number by the IRT at the Screening visit. For subjects who rescreen, the screening number assigned by the IRT at the initial Screening visit should be used. The IRT will assign a randomization number that will encode the subject's treatment assignment according to the randomization schedule generated by the statistics department at AbbVie.

In Part 1, subjects meeting eligibility criteria will be randomized at the Baseline visit to Treatment A through H in a 1:1:1:2:2:2:2:2 ratio. In Part 2, subjects meeting eligibility criteria will be randomized at the Baseline visit to Treatment I through M in a 1:2:2:2:1 ratio. Description of treatment arms are in Section 2.2. In both Part 1 and Part 2, randomization will be stratified by the percent predicted forced expiratory volume in 1 second at Screening visit ( $ppFEV_1 < 70\%$  vs  $ppFEV_1 \geq 70\%$ ). The calculation of percent predicted  $FEV_1$  is described in Section 8.3.1.

To minimize the potential of unblinding, the AbbVie study team will not have access to the post-first-dose spirometry or sweat chloride results until after the study is unblinded for Part 1 or Part 2 analysis. During the blinding phases, the vendors for central reading of the spirometry data or sweat chloride data will only send the blinded files to the sponsor's database to be used for developing the statistical programs.

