## **8.2 Handling of Missing Data**

The primary endpoint and key secondary endpoints will use the same analysis method: Mixed-Effect Model Repeat Measurement (MMRM). This modeling approach handles partially missing dependent variables (change from Baseline to one of the visits is missing) based on the assumption of data being missing at random. No other imputation will be used.

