## **8.4 Secondary Efficacy Analyses**

Efficacy analyses will be performed by treatment group at each protocol-specified visit on each of the secondary efficacy endpoints including

- absolute change from Baseline through Day 29 in Sweat Chloride (in mmol/L),

- absolute change from Baseline through Day 29 in FVC (in L), FEF25-75 (in L/s), and
- relative change, calculated as percent change, from Baseline through Day 29 in ppFEV1, FVC, and FEF25-75

The point estimate for each of the secondary efficacy endpoints from the MMRM model along with the 95% confidence intervals and the corresponding p-values will be presented. In addition, pairwise comparison of each active treatment group versus placebo group will be analyzed using MMRM method as described in Section 8.3.3.

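### The efficacy model names only a random subject effect, by default one variance for all visits, and omits the randomisation stratum; any by-visit intervals are miscalibrated if spread differs between visits

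*SAP*

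**What the plan says.** **Covariance.** SAP 8.3.3 lists treatment, visit and treatment-by-visit as fixed effects and baseline ppFEV1 as a continuous covariate, fitted by REML, and cites the SAS MIXED procedure. On the within-subject part it says "The random effects of the model will be subject ID". Protocol 7.3 has "subject as a random effect". Neither document names a residual covariance structure, a fallback, a degrees-of-freedom method or the visits to be modelled.

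**Where it is used.** SAP 8.1 describes the MMRM results "with the model based mean and standard error being provided". SAP 8.4 opens with "Efficacy analyses will be performed by treatment group at each protocol-specified visit on each of the secondary efficacy endpoints including" (a list follows), then promises an estimate, 95% CI and p-value for each secondary endpoint, and adds that "pairwise comparison of each active treatment group versus placebo group will be analyzed using MMRM method as described in Section 8.3.3".

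**Missing data.** SAP 8.2 relies on the MMRM "based on the assumption of data being missing at random" and uses no other imputation.

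**Stratum.** SAP 2.3 states that "randomization will be stratified by the percent predicted forced expiratory volume in 1 second at Screening visit", split at 70%. SAP 8.1 adds that "any subject who is randomized based on a wrong stratum will be analyzed according to the actual stratum to which the subject belongs". The stratum otherwise appears only in the baseline summaries (SAP 7.1) and the descriptive subgroups (SAP 8.6). It is not a term in the stated model.

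**The concern.** A random subject effect with default residuals is compound symmetry: one variance for every visit and one correlation between visits. Because the standard errors are model-based, that shared variance sets the width of any by-visit interval. If change from baseline is more spread out at one visit, that visit's interval is too narrow and the other's too wide. Either visit could be the more variable one.

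At stake are the by-visit intervals and p-values for sweat chloride, FVC, FEF25-75 and the relative changes, if SAP 8.4 intends them. The primary interval is also at stake if its endpoint is the Day 29 value. With missing data, a wrong covariance also weakens the protection that the missing-at-random assumption is meant to give.

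The stratum is a separate, smaller matter. The trial randomises within strata and has a rule for analysing subjects by actual stratum, but the model does not use the stratum.

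**Working it through.** **Inputs from the documents.** SD of ppFEV1 change 7.5, a single value (SAP 2.4); two-sided alpha 0.05 (SAP 8.1); Part 1 arms 9, 9, 9 and five of 18; Part 2 arms 9, 18, 18, 18, with pooled placebo 18 + 9 = 27.

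**Assumed, because the documents give no figure.** The ratio k of the larger to the smaller visit SD, the correlation between visits, the amount and pattern of missing data, and how the outcome relates to ppFEV1.

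**1. The plan's own power figures.** Noncentral t, two-sided 0.05: one group, n = 18, change 5.3, gives 80.7% (stated 80%). 18 v 18, difference 7.3, gives 81.0% (stated 80%). 18 v 27 gives 87.8% (stated about 87%). They reproduce and do not depend on this point.

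**2. One variance for both visits.** In one simulated Part 1 data set fitted by REML with a random intercept, the two visits received the same SE, 1.847, although their sample SDs were 6.64 and 8.75.

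**3. By-visit coverage.** With complete data the compound-symmetry variance is the mean of the two visit variances. Set it to 1. Then SD_low = √(2/(1+k²)), SD_high = k × SD_low, and coverage = 2Φ(1.96/SD) − 1.

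| k | SD_high | Coverage, more variable visit | SD_low | Coverage, other visit |
|---|---|---|---|---|
| 1.0 | 1.000 | 95.0% | 1.000 | 95.0% |
| 1.1 | 1.046 | 93.9% | 0.951 | 96.1% |
| 1.25 | 1.104 | 92.4% | 0.883 | 97.3% |
| 1.5 | 1.177 | 90.4% | 0.784 | 98.8% |

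The two-sided error at the more variable visit is 100% minus coverage: 6.1%, 7.6% and 9.6% against 5%. These figures do not depend on scale. For ppFEV1 at k = 1.25 and n = 18, the model SE is 7.5/√18 = 1.77 at both visits, against true values of 1.56 and 1.95. No such figure can be given for sweat chloride, FVC or FEF25-75, because the documents state no SD for them.

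**4. Simulation.** 20,000 trials per setting, Part 1 and Part 2 arm sizes, complete data, baseline covariate, Satterthwaite degrees of freedom. Within-group and versus-placebo coverage under compound symmetry was 93.8–94.1%, 92.3–92.7% and 90.3–90.6% at the more variable visit for k = 1.1, 1.25 and 1.5. At the other visit it was 96.0–96.2%, 97.2–97.4% and 98.6–98.7%. With an unstructured covariance it was 94.8–95.2%. The Day 15/Day 29 average under compound symmetry covered 94.9–95.2%.

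**5. Missing data.** SD 7.5, k = 1.5, Day 29 missing by a logistic model in Day 15, compound symmetry by maximum likelihood, 400,000 subjects. The table gives the shift in the two-visit average, in ppFEV1 points.

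| Correlation | Slope per SD of Day 15 | 10% missing | 20% missing |
|---|---|---|---|
| 0.6 | 1 | 0.10 | 0.19 |
| 0.8 | 1 | 0.13 | 0.24–0.25 |
| 0.6 | 2 | – | 0.31 |
| 0.8 | 2 | – | 0.38 |

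Day 15 is complete in these runs, so the Day 29 mean shifts by twice these amounts. With an unstructured covariance the bias was about zero (run at correlation 0.6, slope 1).

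**6. Stratum.** If the stratum explains a share R² of the residual variance, omitting it inflates the SE by 1/√(1−R²) − 1: 0.5%, 1.0%, 2.6% and 5.4% for R² of 1%, 2%, 5% and 10%. With Screening ppFEV1 uniform on 40–90 and an outcome correlation of 0.3–0.5 (assumed), the loss is 0–0.2% if the outcome is linear in ppFEV1 and 1.4–5.4% if it is a pure step at 70%.

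**The case against.** - **SAP 8.4 may not plan by-visit inference.** One sentence puts the analyses at each visit. A later one attaches the interval and p-value to the endpoint, which is defined through Day 29. If that is the two-visit average, the planned interval keeps its coverage. This stands: by-visit intervals are a reasonable reading, not a certainty.
- **The SAP does not choose compound symmetry.** It writes MMRM, and the team may intend an unstructured covariance. A reader might infer a deliberate equal-variance assumption, but the text shows only that no structure is named and that the literal model defaults to one variance.
- **The size is assumed.** No passage suggests that spread differs between two visits 14 days apart. A ratio of 1.5 means 1.5² = 2.25 times the variance; at 1.1 the loss is about one percentage point. This stands, and is why a range is shown.
- **The stratum adds little beyond continuous baseline ppFEV1.** True, and its omission errs towards slightly wide intervals. The misclassification rule in SAP 8.1 also still serves the SAP 8.6 subgroup.
- **The p-values are nominal anyway.** SAP 12.0 plans no multiplicity control. That lowers the stakes, but a reported 95% interval should still cover 95%.

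**Conclusion.** The point holds as a minor one. As written, the model gives all modelled visits one variance and leaves out the randomisation stratum. If SAP 8.4 means intervals at each visit, they under-cover by about 1 to 5 percentage points at the more variable visit and over-cover by about 1 to 4 at the other, for assumed SD ratios of 1.1 to 1.5. At equal SDs there is no effect.

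Three stronger readings are not supported.

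- **The primary analysis is invalid.** With complete data its point estimate is unchanged, and a Day 15/Day 29 average keeps about 95% coverage. Its interval is affected only if the endpoint is the Day 29 value, which the SAP leaves open. With missing data at ratio 1.5, the average shifts by about 0.1 points (10% missing) or 0.2 points (20%) in the milder setting and up to about 0.4 in the strongest one run, against a design change of 5.3.
- **Dose selection is compromised.** No passage ties it to these intervals, and complete-data estimates and dose ranking do not change.
- **Leaving out the stratum biases the comparison.** It does not; it costs under 1% in SE if the outcome is linear in ppFEV1 and up to about 5% under an assumed step at 70%.

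**What to change.** In SAP 8.3.3:

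- Replace the random subject effect by an unstructured covariance over the modelled visits, list those visits, and keep compound symmetry as the fallback if the fit does not converge.
- Add the Screening ppFEV1 stratum as a fixed effect.

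As clarifications:

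- Define the through-Day-29 contrast as the average of Day 15 and Day 29 or as the Day 29 value. This decides whether the primary interval is touched at all.
- Name the degrees-of-freedom method, for example Kenward-Roger.
- State in SAP 8.4 that each secondary model uses that endpoint's own baseline. SAP 8.4 points to a model whose written covariate is baseline ppFEV1. Own baseline is probably intended, since protocol 7.3 asks only for a similar model, but it is not stated.

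The cost is SAP wording and a few lines of code, with no new data. With Day 15 and Day 29 modelled, unstructured needs three covariance parameters instead of two. If the 30-day follow-up is modelled as well (protocol Appendix D schedules sweat collection and spirometry there), it needs six instead of two. The stratum uses one degree of freedom.
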